6.2. Exclusion Criteria

Patients will be excluded from study enrollment if they meet any of the following criteria at Visit 1 (screening) and Visit 6 (enrollment, baseline) unless otherwise specifically defined:

Medical Conditions

- [8] Have had symptomatic herpes zoster infection within 12 weeks prior to Visit 1.
- [9] Have a history of disseminated/complicated herpes zoster (eg, multidermatomal involvement, ophthalmic zoster, central nervous system involvement, post-herpetic neuralgia-).
- [10] Have symptomatic herpes simplex at the time of Visit 1.

- [11] Have evidence of active infection at the time of Visit 1 or during the screening period that, in the opinion of the investigator, would pose an unacceptable risk for participating in the study.
- [12] Have had a serious systemic or local infection (including an infectious mononucleosis-like illness or herpes zoster) within 12 weeks prior to Visit 1 or during the screening -period.

Note: Exceptions include SAVI patients with infected ulcerative skin lesions, which in the opinion of the investigator, would not pose an unacceptable risk for participating in the study.

- [13] Have a risk of TB:

[13a] Have had household contact with a person with active TB and did not receive appropriate and documented prophylaxis for TB.

[13b] Have evidence of active TB or have previously had evidence of active TB defined in this study as the following and did not receive appropriate and documented treatment.

- a positive purified protein derivative (PPD) test (≥ 5 mm induration between approximately 2 and 3 days after application, regardless of vaccination history), and/or QuantiFERON[®]-TB Gold test or T-SPOT[®].TB test (as available and if compliant with local TB guidelines) may be used instead of the PPD test.
 - If the test is not negative, the test may be repeated. If the repeat test results are again not negative, the patient will be considered to have latent TB (for purposes of this study).
- medical history, and
- chest x-ray at screening.

If documented evidence of active TB or have previously had evidence of active TB are available from testing:

- within 3 months before Visit 1 for PPD test, QuantiFERON[®]-TB Gold test, and/or T-SPOT[®].TB test,
- within 6 months before Visit 1 for chest x-ray,

then the patient will not have to be retested at Visit 1.

Exception: patients with a history of active or latent TB who have documented evidence of appropriate treatment, have no history of re-exposure since their treatment was completed, have no clinical features of active TB, and have a screening chest x-ray with no evidence of active TB may be enrolled if other entry criteria met. Such patients would not be required to undergo the protocol-specific TB testing for PPD, QuantiFERON[®]-TB Gold test, or TSPOT[®].TB test but must have a chest x-ray at screening(ie, chest imaging performed within the past 6 months will not be accepted).

[14] Have evidence of, or a positive test for, hepatitis B virus (HBV) infection which is defined as:

- positive for hepatitis B surface antigen (HBsAg),
- positive for hepatitis B core antibody (HBcAb) and detectable HBV DNA,
- positive for hepatitis B surface antibody (HBsAb) and detectable HBV DNA,
- Detectable HBV DNA.

Note: Patients who are positive for HBcAb or HBsAb and negative for HBV DNA may be enrolled in the study. Patients who are HBcAb-, HBsAb+ with a documented history of Hepatitis B vaccination will not be required to undergo HBV DNA testing/monitoring (Section 9.4.6). If results are available from testing within 3 months prior to Visit 1, then the patient will not have to be retested.

[15] Have hepatitis C virus (HCV; positive for anti-hepatitis C antibody with confirmed presence of HCV); have evidence of HIV infection, and/or positive HIV -antibodies.

Note: If results are available from testing within 3 months prior to Visit 1, then the patient will not have to be retested.

[16] Are immunocompromised and, in the opinion of the investigator, are at an unacceptable risk for participating in the study. Additionally, patients with a confirmed diagnosis of *Pneumocystis* pneumonia will be excluded. Patients who have a history of *Pneumocystis* pneumonia will be also excluded if the investigator judges it to be an unacceptable risk.

[17] Have or have had a history of:

- lymphoproliferative disease,
- signs or symptoms suggestive of possible lymphoproliferative disease, or active primary or recurrent malignant disease, or
- been in remission from clinically significant malignancy for <5 years.

Note: Patients with resolved cervical dysplasia, or no more than 3 successfully treated basal-cell- carcinoma of the skin, may participate in this study.

[18] Have any history of venous thromboembolic event (VTE) (deep vein thrombosis [DVT]/pulmonary embolism [PE]) prior to screening.

[19] Have a serious and/or unstable illness that, in the opinion of the investigator, poses an unacceptable risk for the patient's participation in the study.

[20] Have had any major surgery within 8 weeks prior to screening or will require major surgery during the study that, in the opinion of the investigator in consultation with Lilly or its designee, would pose an unacceptable risk to the patient if participating in the trial.

[21] Have screening laboratory test values outside the reference range that, in the opinion of the investigator, pose an unacceptable risk for the patient's participation in the study.

[22] Have any of the following specific abnormalities on screening laboratory tests (patients with NNS/CANDLE will be confirmed the eligibility again using the most recent laboratory test results prior to Visit 6).

- Aspartate aminotransferase (AST) or alanine aminotransferase (ALT) $>2 \times$ the upper limit of normal (ULN),
- Hemoglobin <10 g/dL (100 g/L),
- Total WBC count <2500 cells/ μ L,
- Neutropenia (absolute neutrophil count [ANC] <1200 cells/ μ L),
- Thrombocytopenia (platelets $<100,000/\mu$ L).

Note: The most recent visit prior to Visit 6 is defined as Visit 4 for patients without a biologic agent wash-out or Visit 5 for patient requiring biologic agent wash-out)

Note: A patient with NNS/CANDLE, SAVI, or AGS condition may be enrolled with any of the above specific abnormalities on laboratory tests if these laboratory abnormalities are considered a feature of the disease. If the laboratory abnormality is a feature of the underlying disease must be evaluated, in conjunction with the investigator, and documented; the investigator must also consult with Lilly or its designee before the patient can be enrolled.

[23] Have an eGFR based on serum creatinine at Visit 1 of <40 mL/min/1.73 m²:

- for patients less than 2 years of age (eGFR based on the Bedside Schwarz 2009 formula),
- for patients between 2 years and 18 years of age inclusive (eGFR based on the Japanese Society for pediatric Nephrology formula),
- for patients greater than 18 years of age (eGFR based on CKD-EPI Creatinine 2009 equation)

[24] Have screening thyroid-stimulating hormone and/or thyroxine values outside of the laboratory's reference range and are assessed, in conjunction with the investigator, to be clinically significant.

Note: If results are available from testing within 1 month prior to initial screening, then the patient will not have to be retested. Patients who are receiving thyroxine as replacement therapy may participate in the study, provided stable therapy has been administered for ≥ 3 months and thyroid-stimulating- hormone is within the laboratory's reference range.

Note: In the case of any of the aforementioned laboratory abnormalities (Exclusion criteria [21], [22], [23], and [24]), laboratory tests may be repeated once during the screening period or pretreatment period (only for NNS/CANDEL patients), and values resulting from repeat testing may be accepted for enrollment eligibility if they meet the eligibility criterion.

- [25] Have screening electrocardiogram (ECG) abnormalities that, in the opinion of the investigator, are clinically significant and indicate an unacceptable risk for the patient's participation in the study.
- [26] Have a history of chronic alcohol abuse, intravenous drug abuse, or other illicit drug abuse within the 2 years prior to Visit 1.

Prior/Concomitant Therapy

- [27] Have previously been treated with the following therapies:
 - a. immunosuppressive biologic agent/monoclonal antibody such as:
 - etanercept, infliximab, tocilizumab, certolizumab, adalimumab, golimumab, canakinumab or abatacept within 28 days of Visit 6,
 - rituximab within 6 months of Visit 6.
- Use of intravenous immune globulin is permitted.
- Note: If patients have been treated with any biologics which are not listed above, the investigator must consult with Lilly or its designee. The usage of them may be allowed after discussion with Lilly or its designee.
- b. Any oral JAK inhibitor within 28 days of Visit 6 for SAVI and AGS patients. Patients with NNS/CANDLE must discontinue any oral JAK inhibitor from Visit 1.
- c. Organic Anion Transporter 3 (OAT3) inhibitors with a strong inhibition potential such as probenecid, at the time of Visit 6 that cannot be discontinued for the duration of the study.

- [28] Have been exposed to a live vaccine within the following time period prior to Visit 6
 - 12 weeks for Typhoid and Bacillus Calmette-Guérin (BCG) live vaccines
 - 4 weeks for other live vaccines

OR

Are expected to need/receive a live vaccine during the course of the study .

Note: Young patients who are not yet vaccinated and will be unable to receive live vaccines while receiving baricitinib may be included after discussion with Lilly or its designee.

Note: Booster vaccination for measles, mumps, and rubella or varicella-zoster virus may be considered if it is essential based on the local guideline and/or in the opinion of the -investigator.

Prior/Concurrent Clinical Trial Experience

- [29] Are currently enrolled in any other clinical study involving an investigational product or any other type of medical research judged not to be scientifically or medically compatible with this study
- [30] Have previously been enrolled (received treatment) in this study or any other study investigating baricitinib.
- [31] Have discontinued within 30 days of study entry (Visit 1) from any other clinical study involving an investigational product or any other type of medical research judged not to be scientifically or medically compatible with this study.

Other Exclusions

- [32] Are investigator or site personnel directly affiliated with this study and/or their immediate families. Immediate family is defined as a spouse, parent, child, or sibling, whether biological or legally adopted.
- [33] Are Lilly employees or their designees.
- [34] Are unwilling or unable to make themselves available for the duration of the study and/or are unwilling to follow study restrictions/procedures.

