Study Week	-13	-12	-8	-4
Number of days at visit	-91	-84	-56	-28
Visit tolerance interval (days)		±3	±7	±7
Informed consent/Assent (per local requirements)	X			X
Review inclusion/exclusion criteriab,c	X			X
Demographic characteristics	X			X
Confirmation of genetic mutation related to NNS/CANDLE, SAVI and AGS	X			X
Habits: alcohol, tobacco and caffeine	X			X
Medical history/Preexisting conditions	X			X
Obtain patient's historical data ^d	X			X
Immunization record ^e	X	X	X	X
Concomitant medications	X	X	X	X
Administer PPD/Quantiferon®-TB Gold/T-SPOT®-TB ^f	X			X
Read PPDf	X			X
Chest x-ray ^g	X			X
Physician's Global Assessment of Disease Activity	X	X	X	X
Diary Scores (for NNS/CANDLE, SAVI or AGS)	X	X	X	X
Adverse events	X	X	X	X

NNS/CANDLE						
Screening and Pretreatment						
Visit #	Screening			Pretreatment		
	1	1A	2	3	4	5 a
Study Week	-13	-12	-8	-4	-4	
Number of days at visit	-91	-84	-56	-28		
Visit tolerance interval (days)		±3	±7	±7	±7	
Physical Evaluation						
Vital signs (blood pressure, pulse)	X	X	X	X	X	X
Physical examination ^h	X	X	X	X	X	X
Height	X					
Weight	X			X	X	X
Occipital frontal circumference measurement in children less than 3 years of age	X		X	X	X	
Electrocardiogram	X					
Laboratory tests ⁱ						
Hematology	X		X	X	X	X
Clinical chemistry ^j	X		X	X	X	X
Urinalysis ^k	X					
HBsAg, HBcAb, HBsAb	X					
HBV DNA ^k	X					
Hepatitis C antibody	X					
HIV	X					
Thyroid stimulating hormone	X					
Follicle stimulating hormone ^l	X					
Serum pregnancy test ^m	X					
Urine pregnancy test ^m				X	X	
Samples for biomarkers				X		
hsCRP	X					X

Table JAJE.2. Schedule of Activities (Dose-Adjustment Period, Primary Treatment Period, Maintenance Treatment Period)

NNS/CANDLE		Maintenance Treatment Period											
		Dose-Adjustment Period ⁿ			Primary Treatment Period			Maintenance Treatment Period					
SAVI and AGS		Dose-Adjustment Period ⁿ			Primary Treatment Period			Maintenance Treatment Period					
Visit #	Study Week	6	7	8	9	10	11	12	13	14	15	16	17
		0	2	4	8	12	16	20	24	28	32	36	40
Number of days at visit		1	15	29	57	85	113	141	169	197	225	253	281
Visit tolerance interval (days)			±3	±3	±3	±3			±3				±7
Review inclusion/exclusion criteria ^{b,c}		X ^c											
Immunization records		X	X	X	X	X	X	X	X	X	X	X	X
Concomitant medications		X	X	X	X	X	X	X	X	X	X	X	X
Chest x-ray ^g													
Physician's Global Assessment of Disease Activity		X	X	X	X	X	X	X	X	X	X	X	X
Classification of disease severity (for NNS/CANDLE)		X											X

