- f TB test(s), including PPD, QuantiFERON®-TB Gold, and T SPOT®. PPD tests must be read 48 to 72 hours after screening. If results are available from testing within 3 months, then the patient will not have to be retested.
- g A posterior-anterior chest x-ray is required if it has not been performed in the 6 months prior to screening visit. For the patients who are concerned about a risk of radiation exposure, a chest x-ray will be required at the investigator's discretion if patients have a history of active or latent TB with documented evidence of appropriate treatment or patients have a positive or repeated not-negative TB test(s) (either PPD, QuantiFERON®-TB Gold, and/or T-SPOT®). In addition, chest radiography may be performed at any time during the study, including the follow-up period, if medically necessary, in the opinion of the investigator.
- h One complete physical examination (excluding pelvic and rectal examinations) will be performed at Visit 1. All subsequent physical examinations may be symptom directed. A complete physical examination may be repeated at the investigator's discretion at any time. Fundoscopy may be completed as part of the physical examination, as necessary if, in the opinion of the investigator, it is needed to monitor safety in specific AGS patients. Pulmonary function monitoring for SAVI patients may be completed if medically necessary in opinion of the investigator.
- i In cases where required blood samples cannot be collected due to blood volume limitation relative to patient size/age, the investigator must consult with the Lilly-designated medical personnel to determine which samples to collect. Even if required samples are not collected, it will not be considered a protocol violation, but will need to be documented in the medical record.
- j Clinical chemistry will include eGFR. Patients will receive an initial dose based on weight class and eGFR according to Table JAJE.5. for patients less than 2 years of age (eGFR based on the Bedside Schwarz 2009 formula),
 - for patients between 2 years and 18 years of age inclusive (eGFR based on the Japanese Society for pediatric Nephrology formula),
 - for patients greater than 18 years of age (eGFR based on Chronic Kidney Disease Epidemiology Collaboration [CKD-EPI] Creatinine 2009 equation)

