Patients who meet all of the inclusion criteria (Section 6.1) and do not meet any of the exclusion criteria (Section 6.2) may enter the study (that is, sign consent or assent). In addition, patients must meet the enrollment criteria (Section 6.1) in order to be eligible to receive baricitinib.

Prospective approval of protocol violations to recruitment and enrollment criteria, also known as protocol waivers or exemptions, are not permitted.

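### Schedule footnote g lets a treated-TB patient be screened without a new chest x-ray, which the Exception to exclusion criterion [13] requires

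*Protocol*

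**What the plan says.** **Section 6.2, Exception to criterion [13].** Patients with a history of active or latent TB may enter if four conditions hold: treatment is documented, there has been no re-exposure since it ended, there are no clinical features of active disease, and they "have a screening chest x-ray with no evidence of active TB may be enrolled if other entry criteria met". The next sentence drops the TB test for this group ("Such patients would not be required to undergo the protocol-specific TB testing") and makes the film compulsory: they "must have a chest x-ray at screening(ie, chest imaging performed within the past 6 months will not be accepted". Radiation concern is not mentioned.

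**Section 2, footnote g.** The first sentence requires a chest x-ray only if none was done in the 6 months before the screening visit. The second begins "For the patients who are concerned about a risk of radiation exposure, a chest x-ray will be required at the investigator's discretion if patients have" and goes on to name two groups. One is treated TB, given there as "a history of active or latent TB with documented evidence of appropriate treatment". The other is defined by TB test results and is not at issue here.

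**Section 2, Table JAJE.1 and footnote f.** The Schedule lists a TB test at screening ("Administer PPD/Quantiferon®-TB Gold/T-SPOT®-TB"). Footnote f gives one release: "If results are available from testing within 3 months, then the patient will not have to be retested".

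**Section 6, opening text.** "Prospective approval of protocol violations to recruitment and enrollment criteria, also known as protocol waivers or exemptions, are not permitted".

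**The concern.** Footnote g and the Exception cover the same patients, those whose TB has been treated and documented, and give different instructions about the same film. The footnote is what a site coordinator is likely to consult when planning the screening visit, and it can be followed without noticing that Section 6.2 is stricter.

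The film is one of the conditions on which a patient with past TB may receive a JAK inhibitor, and TB is among the adverse events of special interest in Section 9.2.2. Radiation concern is also realistic in this study, because AGS patients may enter from 6 months of age (Section 6.1, criterion [5b]). A patient entered without the new film would not meet the Exception. That raises the questions of continuing treatment (Section 8.1.3) and of deviation reporting (SAP Section 6.14).

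**Working it through.** No statistical calculation applies. The check sets the two rules side by side for a treated-TB patient, using the two facts on which footnote g turns: whether a film exists from the prior 6 months, and whether there is concern about radiation.

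| Film in prior 6 months? | Radiation concern? | Footnote g | Criterion [13] Exception | Agree? |
|---|---|---|---|---|
| No | No | Film required | New film required | Yes |
| Yes | No | No new film needed (sentence 1) | New film required | No |
| No | Yes | Investigator's discretion (sentence 2) | New film required | No |
| Yes | Yes | No new film needed, or discretion | New film required | No |

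The 2 × 2 = 4 combinations agree in 1 and differ in 4 − 1 = 3. The mismatch is therefore wider than the radiation sentence: sentence 1 alone conflicts with the Exception for any treated-TB patient who has a recent film.

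**Is there reconciling text?** Neither passage refers to the other. Criterion [13] does contain a general 6-month allowance for chest films, but the Exception expressly overrides it for treated-TB patients, so Section 6.2 is consistent within itself. Footnote g carries no such override.

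**Can both texts be obeyed?** Yes, by taking the film. Omitting it satisfies footnote g and fails Section 6.2.

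**What happens to the TB test?** Read alone, the Schedule requires a TB test (new, or within 3 months) and may excuse the film. Read alone, the Exception excuses the test and requires the film. Neither text alone excuses both.

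**The case against.** The strongest reply is that a footnote schedules a procedure while Section 6.2 decides who may enter. All four Exception conditions stay in force whatever footnote g says, and Section 9 requires screening evaluations to be completed and reviewed against every criterion. If a patient slips through, Section 8.1.3 covers inadvertent enrolment, and SAP Section 6.14 gives incorrect enrolment as an example of a deviation and plans a by-patient listing of all important ones. This stands, and it is why the point is minor. It does not make the footnote right: using its discretion to omit the film for this group breaches Section 6.2.

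A second reply concerns meaning. Sentence 2 is awkward and may have been intended to keep the film in view for TB-risk patients while relaxing it for other radiation-concerned patients. Even so, the film remains discretionary where the Exception makes it compulsory. It might also be argued that [13b] excludes only patients lacking documented treatment, so that treated patients never need the Exception. That would leave the Exception without purpose, and its film requirement is mandatory in its own terms.

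Third, no sentence ranks the Schedule against Section 6.2. Section 9 calls adherence to the Schedule essential, and a discretion written into the protocol is not itself a waiver, so the ban on waivers does not settle the matter. This is fair. The case for correcting the footnote rests on Section 6.2 being where eligibility is set and on the film satisfying both texts.

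Two stronger readings are tempting, and the documents support neither. A reader might infer that footnote g makes one of the four entry conditions optional; it amends no criterion. A reader might also infer that a patient could properly enter with neither a TB test nor a film. That would mean borrowing the test release from the Exception while ignoring the film requirement in the same sentence.

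**Conclusion.** The inconsistency is real and confined to patients with treated active or latent TB. Footnote g departs from the Exception through both its 6-month look-back and its radiation discretion. It is a minor safety-consistency error: it could mislead a site about a required film, but it does not change who is eligible, and no endpoint, estimate or planned summary depends on it.

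The number affected is unknown. About 5 patients are planned (Protocol Section 5.2), the documents do not say whether any has treated TB, and few or none is likely. It should not be inferred that anyone was wrongly enrolled.

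The view that screening is complete is an inference. SAP Section 3 records that the 52-week lock has passed, and SAP Section 6.15 ties that analysis to all planned enrolled patients reaching Week 52 or discontinuing earlier. The same revision history places final lock still ahead, so a record check remains useful.

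**What to change.** Add an express exception to footnote g that governs both sentences, for example: *except patients entering under the criterion [13] Exception, who must have a new chest x-ray at screening per Section 6.2*. Do not simply delete treated TB from sentence 2. That would remove the sentence's only prompt to consider a film in this group and would leave the look-back in sentence 1 untouched.

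Before final lock, check the TB screening records of the roughly 5 patients. Handle any entry under the Exception without a new film through Protocol Section 8.1.3 and the important-deviation process in SAP Section 6.14; no new procedure is needed. Footnote g already permits a film at any time if medically necessary, so a safety gap could still be closed, although a later film would not make the original entry compliant.

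The cost is one clause and a short record review. If screening reopened, an affected patient would need one x-ray, which Section 6.2 already requires.
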